6.1.1 Dose Continuation, Modification and Interruption

Subjects will be evaluated for AEs at each visit with the NCI CTCAE v5.0 (Appendix C: NCI CTCAE v5.0) used as a guide for the grading of severity. Refer to the Dose Modification Steps below, and to Sections 6.1.2 and 6.1.3 for full instruction on initiation of a new cycle of therapy and dose modifications during a cycle of therapy.

Dose Modification Steps

Table 1: LENALIDOMIDE Dose Reduction Steps	
Dose Level +1	15 mg daily on Days 1-28 every 28 days
Starting Dose	10 mg daily on Days 1-28 every 28 days
Dose Level – 1	5 mg daily on Days 1-28 every 28 days
Dose Level – 2	5 mg every other day during Days 1-28 every 28 days
Dose Level - 3	Subjects with extended remissions (response > 1 year) may have their dose adjusted at the discretion of the Principal Investigator; any dose adjustments at Dose Level -3 must be approved in writing by the Medical Monitor.

6.1.2 Instructions for initiation of a New Cycle

A new course of treatment may begin on the scheduled Day 1 of a new cycle if:

- The ANC is $\geq 1000 /mm^3$
- The platelet count is $\geq 50,000 /mm^3$;
- Any drug-related rash or neuropathy that may have occurred has resolved to \leq grade 1 severity;
- Any other drug-related adverse events that may have occurred have resolved to \leq grade 2 severity.

If these conditions are not met on Day 1 of a new cycle, the subject will be evaluated weekly and a new cycle of treatment will not be initiated until the toxicity has resolved as described above. If lenalidomide dosing was halted during the previous cycle and was restarted with a one-level dose reduction without requiring an interruption for the remainder of the cycle, then that reduced dose level will be initiated on Day 1 of the new cycle. **If lenalidomide dosing was omitted for the remainder of the previous cycle or if the new cycle is delayed due to toxicity newly encountered on the scheduled Day 1, then the new cycle will be started with a one-level dose reduction of lenalidomide.**

If subjects experience cytopenias and do not meet study requirements to resume lenalidomide, they may proceed with rituximab as described in the protocol.

6.1.3 Instructions for dose modifications or interruption during a cycle

Table 2: Lenalidomide Dose Modifications

NCI CTC Toxicity Grade	Onset Day 2-21 of Cycle	Onset \geq Day 22 of Cycle
Grade 3 neutropenia associated with fever (temperature $\geq 38.5^{\circ}\text{C}$) or Grade 4 neutropenia	
 Hold (interrupt) lenalidomide dose (missed doses of lenalidomide are not made up). Follow CBC weekly. If neutropenia has resolved to \leq grade 2 prior to Day 21, restart lenalidomide at next lower dose level and continue the cycle through Day 28. If neutropenia is the only toxicity for which a dose reduction is required, G-CSF may be used and the lenalidomide dose maintained. 	
 Omit lenalidomide for remainder of cycle See Instructions for Initiation of a New Cycle and reduce the dose of lenalidomide by 1 dose level. If neutropenia is the only toxicity for which a dose reduction is required, G-CSF may be used and the lenalidomide dose maintained for the next cycle at the investigators discretion.
Thrombocytopenia \geqGrade 3 (platelet count $< 50,000/\text{mm}^3$)	
 Hold (interrupt) lenalidomide dose and prophylactic anti-coagulation, if applicable. Follow CBC weekly. If thrombocytopenia resolves to \leq grade 2 prior to Day 21, restart lenalidomide at next lower dose level and continue the cycle through Day 28. See Section 6.3 for instructions for restarting prophylactic anti-coagulation. 	
 Omit lenalidomide for remainder of cycle See Instructions for Initiation of a New Cycle and reduce the dose of lenalidomide by 1 dose level.
Non-blistering rash Grade 3	
 If Grade 3, hold (interrupt) lenalidomide dose. Follow weekly. If the toxicity resolves to \leq grade 1 prior to Day 21, restart lenalidomide at next lower dose level and continue the cycle through Day 28. 	
 Omit lenalidomide for remainder of cycle. See Instructions for Initiation of a New Cycle and reduce the dose of lenalidomide by 1 dose level.
Grade 4	
 Discontinue lenalidomide. Remove patient from study. 	
 Discontinue lenalidomide. Remove patient from study.
Desquamating (blistering) rash- any Grade	
 Discontinue lenalidomide. Remove patient from study. 	
 Discontinue lenalidomide. Remove patient from study.

Table 2: Lenalidomide Dose Modifications

NCI CTC Toxicity Grade	Onset Day 2-21 of Cycle	Onset \geq Day 22 of Cycle
Neuropathy Grade 3	
 Hold (interrupt) lenalidomide dose. Follow at least weekly. If the toxicity resolves to \leq grade 1 prior to Day 21, restart lenalidomide at next lower dose level and continue the cycle through Day 28. 	
 Omit lenalidomide for the remainder of the cycle. See Instructions for Initiation of a New Cycle and reduce the dose of lenalidomide by 1 dose level.
Grade 4	
 Discontinue lenalidomide. Remove patient from study. 	
 Discontinue lenalidomide. Remove patient from study.
Venous thrombosis/embolism \geq Grade 3	
 Hold (interrupt) lenalidomide and start anticoagulation; restart lenalidomide at investigator's discretion (maintain dose level). 	
 Omit lenalidomide for remainder of cycle.
Hyperthyroidism or hypothyroidism	
 Omit lenalidomide for remainder of cycle, evaluate etiology, and initiate appropriate therapy. See Instructions for Initiation of a New Cycle and reduce the dose of lenalidomide by 1 dose level. 	
 Omit lenalidomide for remainder of cycle, evaluate etiology, and initiate appropriate therapy. See Instructions for Initiation of a New Cycle and reduce the dose of lenalidomide by 1 dose level.
other non-hematologic toxicity \geq Grade 3 attributable to lenalidomide	
 Hold (interrupt) lenalidomide dose. Follow at least weekly. If the toxicity resolves to \leq grade 2 prior to Day 21, restart lenalidomide at next lower dose level and continue the cycle through Day 28. 	
 Omit lenalidomide for remainder of cycle. See Instructions for Initiation of a New Cycle and reduce the dose of lenalidomide by 1 dose level.

NOTE: If subjects do not have adequate hematological recovery within 28 days of their last study treatment, lenalidomide will be discontinued and not restarted. However, the subjects will still be followed for response assessment and included in endpoint analyses.

Table 3: Dose Modification for Dexamethasone (Cohort 1 Patients Only)

Use Common Terminology Criteria for Adverse Events (CTCAE) v5.0 unless otherwise specified

CTCAE CATEGORY	ADVERSE EVENT	DOSAGE CHANGE
Gastrointestinal	Dyspepsia, gastric or duodenal ulcer, gastritis Grade 1-2 (requiring medical management)	
Treat with H2 blockers, sucralfate, or omeprazole.
 
If symptoms persist despite above measures, consider dexamethasone dose reduction and/or schedule modification.

Table 3: Dose Modification for Dexamethasone (Cohort 1 Patients Only)		
Use Common Terminology Criteria for Adverse Events (CTCAE) v5.0 unless otherwise specified		
CTCAE CATEGORY	ADVERSE EVENT	DOSAGE CHANGE
	≥Grade 3 (requiring hospitalization or surgery)	Hold dexamethasone until symptoms adequately controlled. Restart dexamethasone at reduced dose along with concurrent therapy with H2 blockers, sucralfate, or omeprazole. If toxicity recurs, discontinuation of dexamethasone may be considered.
	Acute pancreatitis	Discontinue dexamethasone and do not resume
Cardiovascular	Edema ≥Grade 3 (limiting function and unresponsive to therapy or anasarca)	Hold dexamethasone until symptoms adequately controlled. Use diuretics as needed. Restart dexamethasone with consideration of dexamethasone dose reduction and/or schedule modification. If toxicity recurs, discontinuation of dexamethasone may be considered.
Neurology	Confusion or Mood alteration ≥ Grade 2 (interfering with function +/- interfering with activities of daily living)	Hold dexamethasone until symptoms adequately controlled. Restart dexamethasone with consideration of dexamethasone dose reduction and/or schedule modification. If toxicity recurs, discontinuation of dexamethasone may be considered.
Musculoskeletal	Muscle weakness ≥ Grade 2 (symptomatic and interfering with function +/- interfering with activities of daily living)	Hold dexamethasone until symptoms adequately controlled. Restart dexamethasone with consideration of dexamethasone dose reduction and/or schedule modification. If weakness persists, consider further dexamethasone dose reduction and/or schedule modification, or discontinuation.
Metabolic	Hyperglycemia ≥ Grade 3 or higher	Treatment with insulin or oral hypoglycemics as needed. If uncontrolled despite above measures, consider dexamethasone dose modification and/or schedule modification, or discontinuation.
Any Other Toxicity Attributed to Dexamethasone	≥ Grade 3 or higher	Hold dexamethasone until symptoms adequately controlled. Restart dexamethasone with consideration of dexamethasone dose reduction and/or schedule modification. If toxicity recurs, discontinuation of dexamethasone may be considered.

6.2 Rituximab

Rituximab 375mg/m² will be administered by IV infusion once weekly during cycle 3. The initial rate during the first infusion should be 50mg/hr. The infusion rate may be increased, if tolerated, by 50mg/hr increments every 30 minutes to a maximum of 400mg/hr. If administration is well tolerated during the first infusion, subsequent infusions of therapy may begin at a rate of 100 mg/hr. If tolerated, the rate may be increased by 100 mg/hr increments every 30 min to a maximum rate of 400 mg/h.

Close monitoring for tumor lysis syndrome (TLS) and TLS prophylaxis should be initiated during Cycles 1 on Day 3, 4, or 5 and on Day 8. During the Cycle 3, tumor lysis labs should be drawn at one timepoint between days 3-5 and on day 8 after each subject's first dose of rituximab. . Additional assessments may be done at any time (see Sections 3.2 and 6.3). Extra care should be taken with TLS monitoring and with TLS prophylaxis in patients with an absolute lymphocyte count \geq 20,000/ul, and those patients should receive appropriate supportive care (e.g., allopurinol, intravenous hydration, additional laboratory test monitoring, etc.).

6.2.1 Infusion and Hypersensitivity reactions

In subjects with absolute lymphocyte count \geq 20,000/ul, special attention will be given to TLS monitoring and TLS prophylaxis (Section 6.2) and the rituximab infusion shall be modified as follows: 50 mg absolute dose on Day 1, 150 mg absolute dose on Day 2 and (375mg/m²-200mg) on Day 3.

Rituximab infusions must be interrupted if any infusion reactions (e.g., fever, chills, dyspnea etc.) \geq grade 1 occur. When the symptoms have resolved completely, the infusion may be restarted at half the previous rate. If tolerated, rituximab may be gradually re-escalated to the initial infusion rate. If patients experience a second infusion reaction, the rituximab infusion should be stopped. At the investigator's discretion, patients unable to complete the full dose of rituximab may resume the incomplete treatment on the following day after dexamethasone 20 mg po is given the night before and the morning of retreatment.

Infusion reactions are distinct from hypersensitivity reactions, but they may have overlapping manifestations. Hypersensitivity reactions to rituximab are non-IgE mediated and may also respond to decreases in infusion rates. For hypersensitivity reactions \geq grade1, rituximab should be interrupted and the reaction treated with antihistamines, steroids and/or epinephrine. Following complete resolution of grade 1 or 2 reactions, rituximab may be restarted at half the previous rate and re-escalated as above. For grade 3 or 4 hypersensitivity reactions, rituximab should be discontinued.

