5.2 Rituximab (Rituxan®, IDEC-C2B8)

Rituximab is clinically indicated for the treatment of CD20+ non-Hodgkin lymphomas, and will be billed to the patient and/or insurance. Please refer to the agent's package insert for additional information.

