5.2.4 Administration

Rituximab will be administered by IV infusion as described in 6.2. Patients must be pretreated with acetaminophen and diphenhydramine prior to each dose of rituximab.

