6.2.2 Dermatology Toxicity

In the instance of \geq grade 3 erythema multiforme, remove patient from the protocol therapy.

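### Section 6.2.1 allows rituximab to be restarted after a resolved grade 4 infusion reaction but ends it after a grade 4 hypersensitivity reaction, with no rule to tell the two apart

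*Combined protocol and SAP*

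**What the plan says.** Section 5.2.4 makes Section 6.2 the operative text for giving the antibody: "Rituximab will be administered by IV infusion as described in 6.2". Section 5.2 also points outside the protocol: "Please refer to the agent's package insert for additional information".

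Section 6.2.1 handles two kinds of reaction.

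- **Infusion reactions.** Any reaction of grade 1 or higher interrupts the infusion. Then: "When the symptoms have resolved completely, the infusion may be restarted at half the previous rate". For a repeat event: "If patients experience a second infusion reaction, the rituximab infusion should be stopped". The next sentence adds that, at the investigator's discretion, "patients unable to complete the full dose of rituximab may resume the incomplete treatment on the following day", with dexamethasone 20 mg the night before and again that morning.
- **Hypersensitivity reactions.** Restart at half rate is allowed after complete resolution of grade 1 or 2. Above that: "For grade 3 or 4 hypersensitivity reactions, rituximab should be discontinued".

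On the boundary between them the section says only: "Infusion reactions are distinct from hypersensitivity reactions, but they may have overlapping manifestations". It adds that hypersensitivity reactions may also respond to a slower infusion.

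Section 6.2.2 has a further stop, for skin toxicity at or above the grade named: "grade 3 erythema multiforme, remove patient from the protocol therapy".

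Section 5.2.5, a toxicity summary, lists acute respiratory distress syndrome, myocardial infarction, ventricular fibrillation and cardiogenic shock among severe infusion reactions that can be fatal. The same paragraph says that if a reaction occurs the infusion is halted until symptoms resolve and is then restarted at a rate 50% slower.

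**The concern.** The protocol puts its gravest rituximab events under the infusion-reaction label, and that is the label with no grade limit on restarting. The fixed stop for grade 3 and 4 events belongs to the hypersensitivity label. The protocol accepts that the two overlap at the bedside and gives staff nothing to decide between them.

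What is at stake is subject safety. Followed as written, 6.2.1 permits re-exposure after a life-threatening reaction once the symptoms have gone. Whether that happens depends on individual judgement and on the word entered in the chart. For a grade 4 hypersensitivity reaction, the same section does not leave the decision to judgement.

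**Working it through.** The plan states no figure on this point, so there is none to reproduce. The check is a comparison of the rules by label and grade, followed by a count.

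**Step 1. What each label permits once symptoms have resolved (Section 6.2.1).**

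| Grade | Called an infusion reaction | Called a hypersensitivity reaction |
|---|---|---|
| 1–2 | Half-rate restart; next-day resumption possible if the dose was not completed | Half-rate restart |
| 3 | Same as grades 1–2 | Discontinue |
| 4 | Same as grades 1–2 | Discontinue |

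The rules diverge at grade 3 and at grade 4.

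**Step 2. Does any other section close the gap?**

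- Section 4.4 requires removal once the investigator judges that continuing is not in the subject's interest. The trigger is opinion, with no grade attached.
- Section 5.2 cites the package insert for further information. Its content is not in the documents and is not used here.
- Section 5.2.5 repeats the stop-and-restart rule directly after the list of potentially fatal reactions, without a grade limit.
- Table 2 in Section 6.1.3 governs lenalidomide only.
- Section 6.2.2 governs erythema multiforme only.
- The stop after a second infusion reaction applies only after one re-exposure. It is not stated to be permanent, and the next-day resumption sentence follows it.

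None of these sets a grade at which an infusion reaction ends rituximab.

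**Step 3. Count of the statements.**

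- Re-exposure statements that can cover a severe infusion reaction: the first restart sentence in 5.2.5 (1), the half-rate restart in 6.2.1 (1) and the next-day resumption in 6.2.1 (1). 1 + 1 + 1 = 3, of which 0 carry an upper grade. The second restart sentence in 5.2.5 is left out because it concerns less severe reactions.
- Other rituximab reaction rules in 6.2: hypersensitivity grade 3 or 4 (1) and erythema multiforme grade 3 or above (1). 1 + 1 = 2, of which 2 carry a grade-based stop.

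**Step 4. Planned exposure under the rule.** Rituximab is given weekly during the 28-day cycle 3, which is 4 doses (Section 10.1 refers to dose four). Section 8 plans 45 evaluable subjects. 4 × 45 = 180 doses. This is total planned exposure, not a count of expected events.

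**The case against.** The best case for leaving the text alone has four parts.

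1. **The restart rule is meant for mild reactions.** Its examples in 6.2.1 are fever, chills and dyspnea, the same three that 5.2.5 lists as less severe and common. It can be read as routine management of those. But the rule covers *any* infusion reaction from grade 1 up, and 5.2.5 itself classes the life-threatening events as infusion reactions before giving its own restart instruction. The text does not confine the rule to mild events.

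2. **The difference may be intended.** The protocol calls the two reaction types distinct and attributes infusion reactions to cytokine release, so different rules could be a choice. That would be reasonable if staff could tell the two apart. The protocol says they may overlap, offers no test, and gives no reason why a grade 4 event should be treated less strictly under one name.

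3. **Judgement protects the subject.** Restart is permissive and needs complete resolution. Next-day resumption is discretionary and needs steroid cover. Section 4.4 obliges removal once the investigator judges it right. There is also real-time review of adverse events by the principal investigator (11.1), reporting of serious events to the supporter within 24 hours (9.4.1) and a medical monitor (11.2). These safeguards are real and lower the practical risk. All of them rest on judgement or act after the event, and none sets a grade-based stop. The package insert might contain a limit, but that cannot be established from the documents.

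4. **No magnitude is shown and the remedy is partial.** Both points are correct. Counting sentences is not a risk estimate, and a grade 4 cut-off leaves the grade 3 divergence in place. This limits the weight of the point without making the grade 4 rules consistent.

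**Conclusion.** The concern holds. As written, Section 6.2.1 allows re-exposure to rituximab after a resolved grade 4 infusion reaction, while the same section ends rituximab for a grade 4 hypersensitivity reaction, and nothing in the protocol says which label applies.

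The size can be stated only as a property of the text: 0 of 3 re-exposure statements carry an upper grade, against 2 of 2 neighbouring rules with a grade-based stop. The documents give no rate of grade 4 rituximab reactions and none is assumed. Such events may be few: all subjects have received rituximab before (Section 4.1), and 5.2.5 places most reported fatal reactions within a day of the first dose. No effect on the response or progression endpoints is claimed.

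The conclusion rests on reading the protocol's own words, without the package insert. It is a change that should be made, because it is cheap and concerns a life-threatening event, but it does not threaten the trial's analysis. Confidence is medium, given the judgement-based safeguards.

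**What to change.** In Section 6.2.1, add one sentence: after any grade 4 infusion or hypersensitivity reaction, rituximab is permanently discontinued, with no restart and no next-day resumption. In Section 5.2.5, make the restart sentence subject to 6.2.1. Keep the existing grade 3 hypersensitivity stop and leave grade 3 infusion reactions as they are. This removes the dependence on the label at grade 4 only. If the investigators also want it removed at grade 3, they need either a common grade 3 rule or a criterion for separating the two reaction types.

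The cost is that a rare subject who might have tolerated a restart receives less rituximab. Under Section 8 that subject becomes non-evaluable and may be replaced, but stays in the intent-to-treat analysis. The subject also stays in the Section 7.8.2 denominator, because rituximab was received, and in the safety analysis under Section 7.12. The statistical plan needs no change.

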6.2.2 Dermatology Toxicity

In the instance of \geq grade 3 erythema multiforme, remove patient from the protocol therapy.

6.3 Ancillary Therapy

Patients should receive full supportive care, including transfusion of blood and blood products, epoietin, antibiotics, antiemetics etc, when appropriate. The reasons for treatment, dosage and dates of treatment should be recorded.

6.3.1 Tumor Lysis Prophylaxis

Close monitoring for tumor lysis syndrome (TLS) should be initiated concurrently with the initiation of study treatment in Part I for all subjects. Subjects may receive tumor lysis prophylaxis if clinically indicated. All subjects should remain well hydrated during at least the first 7 days of Cycles 1. Close monitoring for TLS and the need for TLS prophylaxis should be repeated during at least the first 7 days of Part II of treatment (the first 7 days of Cycle 3). Additional TLS monitoring and prophylaxis may be employed at any time at the investigator's discretion.

Subjects who are felt to be at high risk for tumor lysis syndrome should receive prophylaxis with allopurinol. Other subjects should receive tumor lysis prophylaxis if clinically indicated. All subjects should be instructed to maintain adequate hydration and maintain urinary output. To maintain fluid intake, subjects should be instructed to drink 8 to 10 eight ounce glasses of water each day for at least the first 7 days of Cycle 1. Hydration levels should be adjusted according to age and clinical status, and lowered if the subject's cardiovascular status indicates the possibility of volume overload. Close monitoring for TLS and TLS prophylaxis (allopurinol, if possible, and oral hydration as above) should be repeated during at least the first 7 days of Part II treatment (the cycle including rituximab). Additional TLS monitoring and prophylaxis may be employed at any time at investigator discretion.

6.3.2 Tumor Flare Reaction

Tumor flare occurring during the first 1-2 weeks of Cycles 1, 2 and 3 should be recorded as AEs and not as progressive disease (PD). Tumor flare should be treated symptomatically with non-steroidal anti-inflammatory agents (NSAIDs) and other measures as needed.

6.3.3 Prophylactic Anti-coagulation

Lenalidomide increases the risk of thrombotic events in patients who are at high risk or with a history a thrombosis, in particular when combined with other drugs known to cause thrombosis. When lenalidomide is combined with other agents such as steroids (e.g. dexamethasone, prednisone), anthracyclines (Doxil, Adriamycin) and erythropoietin the risk of thrombosis is increased. Due to the known increased risk of thrombotic events associated with the combination of lenalidomide and dexamethasone subjects will receive aspirin (81 or 325 mg) or some other form of prophylaxis as deemed appropriate. Low molecular weight heparin may be utilized in patients that are intolerant to ASA. Coumadin should be used with caution and close monitoring of INR. Prophylactic anti-coagulation should be held for platelet counts $< 50,000/\text{mm}^3$ and restarted when platelet counts are $\geq 50,000/\text{mm}^3$. Prophylactic anti-coagulation may be discontinued if dexamethasone is discontinued unless subjects are receiving erythropoietin.

